Attachment 4. Protocol JGDM Biomarker, Pharmacokinetic, and Immunogenicity Blood Sampling Schedule

Cycle	Day	Dosing		Sampling Time (hour) ^a	Olara PK ^b	IGC, ^d	Whole Blood for CTC Analyses	Plasma	Serum	
		Doxorubicin	Olaratumab							
1	1			Within 15 min before Prior to olaratumab infusion ^f	X	X	X	X	X	
			X							
				Within 5 min post olaratumab infusion	X					
	8			Within 15 min before Prior to olaratumab infusion ^f	X	X	X			
		X								
				Within 5 min post olaratumab infusion	X					
2	1			Within 15 min before Prior to infusion ^f	X	X	X	X	X	
			X							
		X								
				Within 5 min post doxorubicin injection	X					
	2			24 hours ± 3 hours	X					
	5			96 hours ± 3 hours	X					
	8				Within 15 min before Prior to olaratumab infusion ^f	X		X		
			X							
					Within 5 min post olaratumab infusion	X				
		9			24 hours ± 3 hours	X				
10			48 hours ± 3 hours	X						
12			96 hours ± 3 hours	X						
18			240 hours ± 3 hours	X						
3	1			Within 15 min before Prior to olaratumab infusion ^f	X	X	X			
			X							
	X									
				Within 5 min post doxorubicin infusion	X					
8				Within 15 min before Prior to olaratumab infusion ^f	X					
		X								
				Within 5 min post olaratumab infusion	X					
5, 7	1			Within 15 min before Prior to olaratumab infusion ^f	X	X				
30-day follow-up				Anytime	X	X	X ^e	X	X	

Abbreviations: CTC = circulating tumor cells; IG = immunogenicity; min = minutes; olara = olaratumab; PK = pharmacokinetic.

- a Time 0 is defined as end of infusion.
- b Samples of approximately 3 mL of whole blood will be drawn into tubes. For the olaratumab samples, olaratumab serum PK measurements will be performed.
- c Samples of approximately 4 mL will be collected.
- d In addition to the scheduled immunogenicity sampling, in the event of an infusion-related reaction, samples are to be collected as close to the onset of the event as possible, at the resolution of the event, and 30 days following the event.
- e At end of the patient's study treatment.
- f Pretreatment PK samples may be collected up to 60 minutes prior to the olaratumab infusion and must be collected prior to administering any premedication.

4.1. Primary Objective

The primary objectives of this study are:

- to enumerate circulating tumor cells (CTCs) changes pre- and post-olatumab monotherapy in wholeblood in patients with potentially resectable soft tissue sarcoma(STS).
- to characterize PDGFR α and platelet-derived growth factor receptor beta (PDGFR β) and canonical ligands (*PDGF-A, B, C, and D*) expression changes pre- and post-olatumab monotherapy in tumor tissue in patients with potentially resectable STS.

4.2. Secondary Objectives

The secondary objectives of this study are:

- to evaluate any antitumor activity observed with olatumab:
 - progression-free survival (PFS) and 3-month PFS
 - ORR (complete response [CR] + partial response [PR])
 - disease control rate (DCR) (CR+ PR + stable disease [SD])
 - rate of resectability.
- to evaluate the safety of olatumab as assessed by reported AEs, clinical laboratory tests, vital signs, physical examinations, electrocardiograms (ECGs), and echocardiograms (ECHOs) or multi-gated acquisition (MUGA) scans.
- to evaluate the pharmacokinetics (PK) of olatumab and immunogenicity (IG) parameters of olatumab.

4.3. Exploratory Objectives

The exploratory objectives of this study are:

- to evaluate blood, CTCs, and tumor tissue pre- and post-therapy for biomarkers related to pathways associated with STS, the mechanism of action (MOA) of olatumab, cancer-related conditions, and/or immune cells/immune and tumor microenvironment functioning within the disease state and/or cancer-related conditions.
- to assess the relationship between biomarker expression at baseline, and change from baseline, and clinical outcomes.

5. A Priori Statistical Methods

5.1. Study Design and Sample Size Consideration

Study JGDM is an open-label, single-arm, multicenter, multicountry Phase 1b study to enumerate whole blood CTCs and to characterize PDGFR α and PDGFR β and canonical ligands (*PDGF-A, B, C* and *D*) expression changes pre- and post-olatumab monotherapy in tumor tissue in patients with potentially resectable STS.

Patients are to be treated with 20 mg/kg of olatumab on Day 1 and Day 8 of Cycle 1, followed by up to 6 cycles (Cycle 2 – Cycle 7) of combination therapy with olatumab plus doxorubicin. For Cycle 2, olatumab is to be dosed at 20 mg/kg on Day 1 and Day 8 and doxorubicin is to be dosed at 75 mg/m² on Day 1. For Cycle 3 – Cycle 7, olatumab is to be dosed at 15 mg/kg on Day 1 and Day 8 and doxorubicin is to be dosed at 75 mg/m² on Day 1. Each cycle of treatment is defined as an interval of 21 days. Approximately 35 patients are to be enrolled.

Starting with the first cycle of combination therapy (Cycle 2), the use of dexrazoxane (in a 10:1 ratio vs. doxorubicin dose) to mitigate cardiotoxicity during treatment with doxorubicin is allowed at the investigator's discretion and is recommended for all patients receiving 5 or more cycles of doxorubicin.

Tissue biopsies are required pre- and posttreatment with olatumab monotherapy. The pretreatment tissue biopsy is to be performed within the screening period. The posttreatment tissue biopsy is to be performed after completion of the lead-in cycle of olatumab monotherapy and prior to the initiation of combination therapy in Cycle 2. An optional third tissue biopsy (or tissue from a posttherapy surgical resection specimen) may be performed at the end of the patient's study treatment. If clinically feasible, the tissue biopsies should be taken from the same primary tumor lesion. If the patient has an additional surgical resection, tissue from this procedure is requested. Refer to Protocol Section 8.2.3.2 for details on tissue biopsies.

Whole blood samples for CTC analyses are to be collected predose at Cycle 1 Day 1 (C1D1), at Cycle 1 Day 8 (C1D8), at Cycle 2 Day 1 (C2D1), at Cycle 2 Day 8 (C2D8), at Cycle 3 Day 1 (C3D1), and at the end of the patient's study treatment or at the time of surgical resection. Refer to Protocol Section 8.2.3.1 for details on blood samples.

After 1 cycle of monotherapy, patients will receive combination therapy for up to 6 cycles or until evidence of progressive disease (PD), unacceptable toxicity, surgical resection, death, or other withdrawal criteria are met. Patients who discontinue study treatment for reasons other than progression or surgical resection will be followed every 6 weeks (± 7 days) until PD. Refer to Protocol Attachment 1 for the Study Schedule.

[figure not shown]
Figure JGDM.1 illustrates the study design.

To investigate the primary objective, approximately 35 evaluable patients have to have completed the pre-treatment tissue biopsy, the predose C1D1 whole blood draw, 1 cycle of olatumab monotherapy, the post-olatumab monotherapy biopsy, and the predose C2D1 whole blood draw.

If the patient is noncompliant during olatumab monotherapy (Cycle 1) and does not undergo

the pre-treatment tissue biopsy, the post-olaparumab monotherapy biopsy, or the predose C2D1 whole blood draw, he or she will be considered nonevaluable and may be replaced. It is hypothesized that 49% (17 out of 35) or more patients will have a reduction of at least 30% in PDGFR α level change in tissue from baseline to post-olaparumab monotherapy. The sample size of 35 patients provides a 95% CI that the hit rate (proportion of patients with at least 30% reduction in PDGFR α level change from baseline) will be between 31% and 66%, which excludes a 30% or lower hit rate.

Figure JGDM.5.1 Illustration of study design

Abbreviations: C1D1 = Cycle 1 Day 1; C2D1 = Cycle 2 Day 1; C3D1 = Cycle 3 Day 1; CTC = circulating tumor cell; D = day(s); ECOG PS = Eastern Cooperative Oncology Group performance status; STS = soft tissue sarcoma, tx = treatment.

^a The pre- and post-olaparumab monotherapy tissue biopsies and the whole blood sample collections pre-dose at C1D1, C1D8, C2D1, and C2D8 for CTC analyses are mandatory. The pre-olaparumab monotherapy biopsy is to be collected within the screening period. The post-olaparumab monotherapy biopsy is to be collected after completion of Cycle 1 and prior to initiation of Cycle 2 combination therapy. If clinically feasible, the biopsies should be taken from the same primary tumor lesion.

^b An optional third tumor tissue biopsy is to be collected at the end of the patient's study treatment or when the patient undergoes a surgical resection through which a posttherapy tissue specimen can be collected. If clinically feasible, the biopsies should be taken from the same primary tumor lesion. Additionally, a whole blood sample for CTC analysis is to be collected at C3D1 and at the end of the patient's study treatment or at the time of surgical resection. ^c See text in protocol Section 6.2, Summary of Study Design.

Note: Each cycle of treatment is defined as an interval of 21 days.

5.2. General Considerations

Statistical analysis of this study will be the responsibility of Eli Lilly and Company (Lilly). The analyses for this study will be descriptive, except for possible exploratory analysis as deemed

appropriate. Data analyses will be provided by cycle (cycle 1 versus cycle 2 onward) for specified analyses and for all study patients combined wherever appropriate. For continuous variables, summary statistics will include number of patients, mean, median, standard deviation, minimum, and maximum. Categorical endpoints will be summarized using number of patients, frequency, and percentages. Unless otherwise specified, missing data will not be imputed.

The interpretation of the study results will be the responsibility of the investigator with the Lilly Clinical Research Physician (CRP)/Clinical Research Scientist (CRS), pharmacokineticist, and statistician. The CRP or CRS and statistician will also be responsible for the appropriate conduct of an internal review for both the final study report and any study-related material to be authorized by Lilly for publication.

Exploratory analyses of the data not described below will be conducted as deemed appropriate.

5.3. Definitions of Analysis Variables

Definitions of safety and efficacy analysis variables are listed in Section 5.3.1 and Section 5.3.5, respectively.

The general analysis variables are listed below alphabetically.

- **Age (years):** $(\text{Informed Consent Date} - \text{Date of Birth} + 1)/365.25$.

Note. Average days in a year = 365.25, reflecting the Julian Year of 3 years with 365 days each and 1 leap year of 366 days. Birth month and day are imputed to be 01 July because only birth year is collected through the case report form (CRF).

- **Baseline measurement:** The last non-missing measurement prior to or on the first dose date will serve as the baseline measurement.
- **Duration is calculated as:**
 - Duration (days): $(\text{End Date} - \text{Start Date} + 1)$
 - Duration (weeks): $(\text{End Date} - \text{Start Date} + 1)/7$
 - Duration (months): $(\text{End Date} - \text{Start Date} + 1)/30.4375$
 - Duration (years): $(\text{End Date} - \text{Start Date} + 1)/365.25$
- **Study Day:** Study day indicates the number of days relative to the date of first dose. It is calculated as assessment date – first dose date + 1 day if the assessment is done on or after the first dose day. If the assessment is done prior to the first dose day, study day will be calculated as assessment date – first dose date. Date of first dose is defined as Study Day 1.

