After 1 cycle of monotherapy, patients will receive combination therapy for up to 6 cycles or until evidence of progressive disease (PD), unacceptable toxicity, surgical resection, death, or other withdrawal criteria are met. Patients who discontinue study treatment for reasons other than progression or surgical resection will be followed every 6 weeks (± 7 days) until PD.

Refer to [Attachment 1](#) for the Study Schedule.

[Figure JGDM.1](#) illustrates the study design.

Abbreviations: C1D1 = Cycle 1 Day 1; C2D1 = Cycle 2 Day 1; C3D1 = Cycle 3 Day 1; CTC = circulating tumor cell; D = day(s); ECOG PS = Eastern Cooperative Oncology Group performance status; STS = soft tissue sarcoma, tx = treatment.

^a The pre- and post-olaratumab monotherapy tissue biopsies and the whole blood sample collections pre-dose at C1D1, C1D8, C2D1, and C2D8 for CTC analyses are mandatory. The pre-olaratumab monotherapy biopsy is to be collected within the screening period. The post-olaratumab monotherapy biopsy is to be collected after completion of Cycle 1 and prior to initiation of Cycle 2 combination therapy. If clinically feasible, the biopsies should be taken from the same primary tumor lesion.

^b An optional third tumor tissue biopsy is to be collected at the end of the patient's study treatment or when the patient undergoes a surgical resection through which a posttherapy tissue specimen can be collected. If clinically feasible, the biopsies should be taken from the same primary tumor lesion. Additionally, a whole blood sample for CTC analysis is to be collected at C3D1 and at the end of the patient's study treatment or at the time of surgical resection.

^c See text in Section 6.2, Summary of Study Design.

Note: Each cycle of treatment is defined as an interval of 21 days.

Figure JGDM.1. Illustration of study design.

Terms used to describe the periods during the study are defined below:

- **Baseline:** begins when the ICF is signed (study entry) and ends at the first study treatment (or at discontinuation, if no treatment is given).
- **Study Period:** begins at the first study treatment and ends at study completion.
 - **Study Treatment Period:** begins at the first study treatment and ends when the patient and the investigator agree that the patient will no longer continue study

treatment. The date of this agreement is to be reported on the electronic case report form (eCRF) as the Date of Discontinuation from study treatment.

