7.2.1. Treatments Administered

Table JGDM.1 shows the treatment regimens to be administered in this study.

Table JGDM.1. Treatment Regimens

Treatment	Cycle Length (Days)	Study Drug	Dose	Timing	Route
Monotherapy Cycle 1	21	Olaratumab ^a	20 mg/kg	approximately 1 hour infusion D1, D8	IV
		1-hour (\pm 5 minutes) Observation Period ^b			
Combination Therapy Cycle 2	21	Olaratumab ^a	20 mg/kg	approximately 1 hour infusion D1, D8	IV
		1-hour (\pm 5 minutes) Observation Period ^b followed by			
		Doxorubicin ^c	75 mg/m ²	IV injection on D1	IV
Combination Therapy Cycle 3 – Cycle 7	21	Olaratumab ^a	15 mg/kg	approximately 1 hour infusion D1, D8	IV
		Doxorubicin ^c	75 mg/m ²	IV injection on D1	IV

Abbreviations: D = day; eCRF = electronic case report form; IRR = infusion-related reaction; IV = intravenous; PO = orally.

- ^a Premedicate all patients with the following (or equivalent) medications: a histamine H1 antagonist (for example, diphenhydramine) and dexamethasone intravenously 30–60 minutes prior to the olaratumab doses on Days 1 and 8 of Cycle 1. For subsequent cycles, premedicate all patients with a histamine H1 antagonist (for example, diphenhydramine) intravenously 30–60 minutes prior to each dose of olaratumab. Additional premedication may be provided at the investigator's discretion. Premedication **must be** provided in the setting of a prior Grade 1-2 IRR, as detailed in Section 7.2.2 and Section 7.2.3.1.1.1. All premedication administered must be adequately documented in the eCRF.
- ^b A 1-hour (+5 minutes) Observation Period is required after the administration of the initial 2 cycles of olaratumab. During the Observation Period, collect vital signs 3 times: 1) within 15 minutes (+5 minutes) prior to olaratumab infusion, 2) within 1 hour (+5 minutes) after completion of the olaratumab infusion, and 3) within 1 hour (+5 minutes) after completion of the doxorubicin infusion. If no evidence of an IRR manifests during the initial 2 cycles of olaratumab, then no observation period is required for subsequent treatment cycles. In the event an IRR occurs thereafter, then the 1-hour Observation Period should be reinstated; see Section 7.1.2. Thereafter (Cycles 3+), obtain vital signs 2 times: 1) within 15 minutes (+5 minutes) prior to olaratumab infusion and 2) within 1 hour (+5 minutes) after completion of the doxorubicin infusion.

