	6.1	Vital Signs	X	X	X	X	Vital signs include blood pressure, pulse, and temperature. During the Observation Period (initial 2 cycles of olaratumab therapy), collect vital signs 3 times: 
 • within 15 minutes (+5 minutes) prior to olaratumab infusion • within 1 hour (+5 minutes) after completion of the olaratumab infusion • within 1 hour (+5 minutes) after completion of the doxorubicin infusion. Thereafter (Cycles 3+), obtain vital signs 2 times: within 15 minutes (+5 minutes) prior to olaratumab infusion within 1 hour (+5 minutes) after completion of the doxorubicin infusion.		
Lab/ Diagnostic Tests	Attachment 2	Hematology	X	X	X	X	Laboratory assessments may be done within 7 days prior to D1 and D8 of each cycle. See Attachment 2 for details. Testing will be performed locally for patient management and centrally for analysis purposes.		
	Attachment 2	Serum Chemistry	X		X		Laboratory assessments may be done within 7 days prior to D1 of each cycle. See Attachment 2 for details. Testing will be performed locally for patient management and centrally for analysis purposes.		
	Attachment 2	Coagulation Profile	X		X		Perform on D1 every other cycle or as clinically indicated. See Attachment 2 for details. Testing will be performed locally only.		
	Attachment 2	Urinalysis	X		X		Laboratory assessments may be done within 7 days prior to D1 of every other cycle or as clinically indicated. Includes a routine UA, and, if clinically indicated, a microscopic analysis. If routine analysis indicates >2+ proteinuria, then a 24-hour urine must be collected and must demonstrate ≤1000 mg of protein in 24 hours. Testing will be performed locally only.		
	Attachment 2	Pregnancy Test	X		X		Serum β-HCG or urine pregnancy test on D1 of every cycle or per local practice (whichever is of shorter duration). If a pregnancy test performed on D1 of the cycle is positive, confirm with a serum or urine pregnancy test (pregnancy test results are not recorded on the eCRF). If results are positive, the investigator is to consult with the Lilly CRP. Testing will be performed locally only.		
	8.2.2 Attachment 4	PK Samples	See Attachment 4 for specific time points					Whole blood samples collected for olaratumab serum PK measurements.	

Procedure Category	Protocol Section	Procedure	Study Period				Treatment Period				Comments

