Premedication	7.2.2	Administer premedication prior to olaratumab treatment	X	X	X	X	Premedicate all patients with the following medications (or equivalent): a histamine H1 antagonist (eg, diphenhydramine) and dexamethasone intravenously 30–60 minutes prior to the olaratumab doses on Days 1 and 8 of Cycle 1. For subsequent cycles, premedicate all patients with a histamine H1 antagonist (eg, diphenhydramine) intravenously 30-60 minutes prior to each dose of olaratumab.	
	7.2.2	Administer dexrazoxane prior to doxorubicin			X		Dexrazoxane is recommended for all patients receiving 5 or more cycles of doxorubicin.	
Study Treatment	7.1.2	Administer olaratumab	X	X	X	X	Administer through completion of Cycle 7 or until PD, surgical resection, unacceptable toxicity, death, or other withdrawal criteria are met.	
	7.1.3	Administer doxorubicin			X		Administered to all patients during combination therapy for up to a maximum of 6 cycles (Cycles 2-7) (unless previous unacceptable toxicity).	
Patient Disposition			X		X		At the time that the patient is discontinued from any component of the study treatment or study participation, information regarding the patient status will be collected.	

Abbreviations: β -HCG = beta human chorionic gonadotropin; AE = adverse event; BSA = body surface area; C = cycle; CR = complete response; CRP = clinical research physician; CT = computed tomography; CTCAE = Common Terminology Criteria for Adverse Events; D = day; DNA = deoxyribonucleic acid; ECG = electrocardiogram; ECOG = Eastern Cooperative Oncology Group; eCRF = electronic case report form; IRR = infusion-related reaction; LVEF = left ventricular ejection fraction; MRI = magnetic resonance imaging; MUGA = multi-gated acquisition; PD = progressive disease; PET = positron emission tomography; PK = pharmacokinetic; PR = partial response; RECIST = Response Evaluation Criteria in Solid Tumors; SD = stable disease; UA = urinalysis.

- a Study procedures will be performed prior to study drug administration, except where noted (such as vital signs). In case of dose interruption, these evaluations will also be done at minimum frequency every 21 days (± 3 days).
- b Relative day within each cycle (≤ 3 days). Procedure allowed up to 3 days before D1.

Posttreatment Discontinuation Follow-Up Schedule of Activities

Procedure Category	Protocol Section	Procedure	Posttreatment Discontinuation Follow-Up		Comments
			Study Period		
			Short-Term Follow-Up	Long-Term Follow-Up	
			Visit		

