Attachment 2. Protocol JGDM Clinical Laboratory Tests

All laboratory screening evaluations are to be performed within 14 days prior to enrollment, unless otherwise specified. Eligibility for inclusion in this clinical trial will be based on local clinical laboratory results (not transcribed onto electronic case report forms); duplicate samples will be submitted to the central laboratory. Treatment decisions may be based upon results of tests performed locally. Discrepancies between local and central laboratory that may have an impact on eligibility or treatment decisions will not be considered protocol deviations. On-study clinical laboratory tests assayed for patient safety (such as hematology, serum chemistry, coagulation, and pregnancy tests) are to be collected prior to study treatment.

Clinical Laboratory Tests**Hematology^{a,b}**

Hemoglobin
 Hematocrit
 Erythrocyte count (RBC)
 Mean cell volume
 Mean cell hemoglobin concentration
 Leukocytes (WBC)
 Neutrophils
 Lymphocytes
 Monocytes
 Eosinophils
 Basophils
 Platelets

Coagulation Test^a

Prothrombin time (PT)
 Partial Thromboplastin Time (PTT)
 International normalized ratio (INR)

Urinalysis^{a,c}

Specific gravity
 pH
 Protein
 Glucose
 Ketones
 Blood

Urine leukocyte esterase

Other^d

Immunogenicity samples
 PK samples
 Biomarker samples

Clinical Chemistry^{a,b}**Serum Concentrations of the following:**

Sodium
 Potassium
 Total bilirubin
 Alkaline phosphatase
 Alanine aminotransferase (ALT)
 Aspartate aminotransferase (AST)
 Blood urea nitrogen (BUN)
 Creatinine
 Uric acid
 Calcium
 Glucose, random
 Albumin
 Total protein
 Chloride
 Thyroid-stimulating hormone
 Direct bilirubin

Pregnancy test^{a,c}**Follicle-stimulating hormone (FSH)^{a,f}**

Abbreviations: CRP = clinical research physician; D = Day; PK = pharmacokinetics; RBC = red blood cells; WBC = white blood cells

- a Assayed by local or investigator-designated laboratory.
- b Duplicate samples will also be assayed by a sponsor-designated laboratory.
- c If urinary protein is $\geq 2+$ at evaluations, a 24-hour urine collection (to assess protein) must be collected and must be ≤ 1000 mg of protein in 24 hours (up to 3 business days is allowed if the weekend).
- d Assayed by a sponsor-designated (central) laboratory.

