5.11.4. Vital Signs, Physical Findings, and Other Observations Related to Safety

Actual value and change from baseline for vital sign measurements will be summarized at each assessment time point using summary statistics. Electrocardiogram, Echocardiogram(ECHO)/MUGA measurements will also be summarized at each assessment time point using summary statistics. Listings of vital signs, ECG, ECHO/MUGA and data will be provided.

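### For vital signs, the SAP's date-based baseline selects the post-infusion reading on Cycle 1 Day 1, so change from baseline is measured from an on-treatment value

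*SAP*

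**What the plan says.** SAP 5.3 lists baseline among the general analysis variables: "The last non-missing measurement prior to or on the first dose date will serve as the baseline measurement". The test is the date alone; neither clock time nor position relative to the infusion enters. SAP 5.11.4 then plans: "Actual value and change from baseline for vital sign measurements will be summarized at each assessment time point using summary statistics". It gives no separate baseline rule for vital signs.

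Protocol Attachment 1 sets the readings: "During the Observation Period (initial 2 cycles of olaratumab therapy), collect vital signs 3 times". The first is "within 15 minutes (+5 minutes) prior to olaratumab infusion" and the second is "within 1 hour (+5 minutes) after completion of the olaratumab infusion" (also in footnote b to Table JGDM.1, Protocol 7.2.1). The third follows doxorubicin. A footnote to the on-treatment schedule makes vital signs the named exception to pre-dose collection: "Study procedures will be performed prior to study drug administration, except where noted (such as vital signs").

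Protocol 6.2 defines the baseline period as one that "begins when the ICF is signed (study entry) and ends at the first study treatment".

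**The concern.** Including the first dose date is harmless, even useful, when everything measured that day is measured before dosing: it lets the Day 1 pre-dose sample count as baseline. It fails for any variable measured both before and after the dose on that day, because the last value on the date is then an on-treatment value. Vital signs are such a variable by design.

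Vital signs are part of the secondary safety objective. Infusion-related reactions are the adverse event of special interest for olaratumab, and Protocol 7.2.2 reports that the severe ones have occurred mainly in the first cycle. The change across the first infusion is therefore the vital-sign contrast a reader is most likely to look up. Under the stated rule that row carries no information, and the rows below it are displaced.

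**Working it through.** The plan states no figure on this point, so there is none to reproduce. The check applies the rule to the schedule.

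**Step 1: which reading is baseline?** Doxorubicin starts in Cycle 2 (Protocol 6.2 and Table JGDM.1), so the third reading does not arise on Cycle 1 Day 1. Two scheduled readings fall on the first dose date: pre-infusion (value P) and post-infusion (value P - d, where d is the fall across the first infusion; a negative d is a rise). Both satisfy the date test. The last is the post-infusion one, so

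- baseline under SAP 5.3: B = P - d
- baseline under a pre-dose rule, consistent with Protocol 6.2: B = P

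**Step 2: change from baseline, value minus B.**

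- Day 1 post-infusion: SAP (P - d) - (P - d) = 0; pre-dose rule (P - d) - P = -d
- Day 8, recovered to P: SAP P - (P - d) = +d; pre-dose rule P - P = 0
- Any later value X: SAP X - (P - d) = (X - P) + d, which is the pre-dose change displaced by d

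**Step 3: numbers.** The documents give no expected vital-sign change. The values below are assumptions: systolic pressure 130 mmHg before infusion, falls of 5 to 40 mmHg, full recovery by Day 8.

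| Assumed fall d | Baseline, SAP | Baseline, pre-dose | Day 1 post: SAP / pre-dose | Day 8: SAP / pre-dose |
|---|---|---|---|---|
| 5 | 125 | 130 | 0 / -5 | +5 / 0 |
| 10 | 120 | 130 | 0 / -10 | +10 / 0 |
| 20 | 110 | 130 | 0 / -20 | +20 / 0 |
| 40 | 90 | 130 | 0 / -40 | +40 / 0 |

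The Day 1 post-infusion row has mean 0 and standard deviation 0 whatever happened, because each patient in it is compared with the same reading. If a Day 1 pre-infusion row is tabulated, it shows 130 - (130 - d) = +d: the infusion effect with its sign reversed.

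**Step 4: missing readings.** A patient with no post-infusion reading on Day 1 falls back to the pre-infusion value, so B = P. One column of the table then mixes two references. If a share m of patients lacks the reading, the displacement of a later mean is (1 - m) times the average d among those who have it.

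**Step 5: what else does the rule touch?** Attachment 2 says on-study safety laboratory tests "are to be collected prior to study treatment". The scheduled Cycle 1 Day 1 circulating-tumor-cell, plasma and serum samples are pre-infusion (Attachment 4), and the pretreatment biopsy is taken in screening. ECGs fall under the general pre-dose footnote. For all of these the date rule still selects a pre-dose value.

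**The case against.** The strongest reply is that little depends on this column. The study is single-arm and descriptive; no test, primary endpoint or stopping rule uses vital-sign change. Actual values at each time point and listings are also planned (SAP 5.11.4). An experienced programmer would probably take the pre-dose record, as Protocol 6.2 implies. All of this limits the consequence. It does not rescue the rule, which expressly includes the dose date; taking the pre-dose record would depart from the SAP as written.

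Three stronger readings are tempting and are not supported:

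- **That first-infusion reactions would be hidden.** They are graded by CTCAE definition (Protocol 7.2.3.1.1.1) and summarized and listed as adverse events of special interest (SAP 5.11.2). SAP 5.13 adds antibody listings for patients with a reaction. None of these uses the vital-sign baseline.
- **That the post-infusion reading contains any reaction to the drug.** For a Grade 1 or 2 reaction the infusion is stopped, the patient is treated, and the infusion resumes after recovery (Protocol 7.2.3.1.1.1). A reading after completion may therefore be normal. A Grade 3 or 4 reaction ends olaratumab permanently, so a patient with one on Day 1 would contribute no later olaratumab-infusion readings.
- **That the displacement is large in all of the roughly 35 patients.** The rule picks the wrong record in every patient with a post-infusion reading, but the size of the shift is that patient's d, about which the documents say nothing.

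**Conclusion.** The point holds, confined to vital signs. As written, SAP 5.3 selects an on-treatment reading as baseline and disagrees with Protocol 6.2. The Day 1 post-infusion change is 0 by construction, later changes are displaced by the first-infusion change, and the reference varies with whether the post-infusion reading is present. The 5 to 40 mmHg range only illustrates the arithmetic; if the average first-infusion change is small, so is the displacement of the means.

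This assumes that the scheduled post-infusion reading is the last one on Day 1. A later unscheduled reading would become baseline instead, and would equally be on treatment. It also assumes that the sentence is applied literally. The primary biomarker analyses, scheduled laboratory baselines and reporting of infusion-related reactions are unaffected. Label: wrong as written, free to fix.

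**What to change.** Replace the baseline sentence in SAP 5.3 with: the last non-missing measurement taken before the start of the first study-drug infusion. Add that order is decided by the actual collection time, which Protocol 8.4 requires on the eCRF for safety assessments, and, where that time is absent, by the scheduled pre-infusion record. A patient with no pre-infusion reading on Day 1 then uses the last screening value.

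The cost is one SAP sentence and a matching line in the programming specification. No protocol amendment or data collection beyond what the protocol already requires is needed, and baselines for scheduled pre-dose assessments do not change. The documents do not show the eCRF fields, so confirm that the pre- and post-infusion vital-sign records can be told apart when a time is missing.
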